#### 12.7.5 Response Criteria for Non-Target Lesions:

- **Complete Response (CR):** Disappearance of all non-target lesions.
- **Incomplete Response/Stable Disease (IR/SD):** The persistence of one or more non-target lesions.
- **Progressive Disease (PD):** The appearance of one or more new lesions and/or unequivocal progression of existing non-target lesions.

#### 12.7.6 Response criteria for tumor markers (if available):

Tumor markers will be classified simply as being at normal levels or at abnormally high levels.

**12.7.7 Overall Response Assessment**

The overall response assessment takes into account response in both target and non-target lesions, the appearance of new lesions and normalization of markers (where applicable), according to the criteria described in the table below. The overall response assessment is shown in the last column, and depends on the assessments of target, non-target, marker and new lesions in the preceding columns.

Target Lesions	Non-target Lesions	Markers	New Lesions	Overall Response
CR	CR	Normal	No	CR
CR	IR/SD	Normal	No	PR
CR	CR, IR/SD	Abnormal	No	PR
PR	CR, IR/SD	Any	No	PR
SD	CR, IR/SD	Any	No	SD
PD	Any	Any	Yes or No	PD
Any	PD	Any	Yes or No	PD
Any	Any	Any	Yes	PD

Each patient will be classified according to his “best response” for the purposes of analysis of treatment effect. Best response is determined as outlined in [Section 12.9](#) from a sequence of overall response assessments.

**12.8 Response Criteria for Patients with non- Hodgkin Lymphoma/Histiocytosis**

Response and progression will be evaluated in this study using the new international criteria proposed by the revised Response Evaluation Criteria in Pediatric non-Hodgkin Lymphoma Criteria, with modification from the Lugano classification.

**12.8.1 Disease Parameters**

12.8.1.1 **Measurable disease:** A measurable node must have an LDi (longest diameter) greater than 1.5 cm. A measurable extranodal lesion should have an LDi greater than 1.0 cm. All tumor measurements must be recorded in millimeters (or decimal fractions of centimeters).

12.8.1.2 **Non-measured disease:** All other lesions (including nodal, extranodal, and assessable disease) should be followed as nonmeasured disease (e.g., cutaneous, GI, bone, spleen, liver, kidneys, pleural or pericardial effusions, ascites).

12.8.1.3 **Target lesions:** For patients staged with CT, up to six of the largest target nodes, nodal masses, or other lymphomatous lesions that are measurable in two diameters (longest diameter [LDi] and shortest diameter) should be identified from different body regions representative of the patient’s overall disease burden and include mediastinal and retroperitoneal disease, if involved.

### 12.8.2 Evaluation of Measurable Disease

#### Complete Response (CR)

*Disappearance of all disease.* CT or MRI should be free of residual mass or evidence of new disease. FDG-PET should be negative.

#### Complete Response Unconfirmed (CRu)

Residual mass is negative by FDG-PET; no new lesions by imaging examination; no new and/or progressive disease elsewhere

#### Partial Response (PR)

50% decrease in SPD (the sum of the products of the largest diameter and the perpendicular diameter for a tumor mass) on CT or MRI; FDG-PET may be positive (Deauville score of 4 or 5 with reduced lesional uptake compared with baseline); no new and/or PD; morphologic evidence of disease may be present in BM if present at diagnosis; however, there should be 50% reduction in percentage of lymphoma cells.

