- 1 Women of childbearing potential require a negative pregnancy test prior to starting treatment; sexually active patients must use an acceptable method of birth control. Abstinence is an acceptable method of birth control.
- 2 If patients have Grade 4 neutropenia then CBCs should be checked at least every other day until recovery to Grade 3 or until meeting the criteria for dose limiting toxicity.
- 3 If patients develop Grade 3 or greater thrombocytopenia then CBCs should be checked every 3 to 4 days until recovery per [Section 6.1](#).
- 4 Tumor Disease Evaluation should be obtained on the next consecutive cycle after initial documentation of either a PR or CR. Subsequent scans may restart 2 cycles after the confirmatory scan. If the institutional investigator determines that the patient has progressed based on clinical or laboratory evidence, he/she may opt not to confirm this finding radiographically.
- 4-A Neurological exam is also required for CNS patients.
- 4-B Non-Hodgkin Lymphoma/ Histiocytosis patients are required to have PET scans within 2 weeks prior to start of therapy and should also be followed with PET scans if positive at diagnosis. Refer to [Section 12.8](#).
- 4-C Patients with neuroblastoma must have both CT/MRI and MIBG scintigraphy prior to the start of therapy if the patient was enrolled with or has a history of having MIBG avid tumor. Otherwise the patient must have both CT/MRI and bone scan prior to the start of therapy. For patients with neuroblastoma and measurable disease by CT or MRI, lesions should be measured and followed using the same modality (CT or MRI) in addition to MIBG or bone scan. For patients with neuroblastoma and evaluable disease by MIBG scintigraphy or bone scan, use the same modality (MIBG scintigraphy or bone scan) to image and follow patients; CT/MRI are not required but may be performed as clinically indicated. Refer to [Section 12.5.4](#) and [Section 12.9](#).
- 5 Bone marrow aspirate and/or biopsy only required in patients suspected of having bone marrow metastasis on the basis of history, symptoms, laboratory evaluation or other clinical data.
- 6 Bone marrow aspirate and/or biopsy should be performed only when complete response or partial response is identified in target disease or when progression in bone marrow is suspected.
- 7 Medication diary (see [Appendix III](#)) should be reviewed weekly during cycle 1, after completion of each treatment cycle and uploaded into RAVE.

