#### Progressive disease

For those with > 25% increase in SPD on CT or MRI, Deauville score 4 or 5 on FDG-PET with increase in lesional uptake from baseline, or development of new morphologic evidence of disease in BM

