### 12.8.4 Evaluation of organ enlargement

Complete Response (CR): Regress to normal

Partial response (PR): Spleen must have regressed by >50% in length beyond normal

Stable Disease (SD): No increase consistent with progression

Progressive Disease (PD): In the setting of splenomegaly, the splenic length must increase by 50% of the extent of its prior

increase beyond baseline. If no prior splenomegaly, must increase by at least 2 cm from baseline.

New or recurrent splenomegaly

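### The lymphoma/histiocytosis criteria tie marrow and PET rules to diagnosis instead of study entry, and the spleen PR and PD rows use different, partly undefined reference points

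*Combined protocol and SAP*

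**What the plan says.** **Marrow, PR (12.8.2).** Besides a 50% fall in SPD, the definition states that "morphologic evidence of disease may be present in BM if present at diagnosis; however, there should be 50% reduction in percentage of lymphoma cells". The same definition judges PET by "reduced lesional uptake compared with baseline", and it also requires "no new and/or PD".

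**Marrow, PD (12.8.2).** The only marrow event listed is "or development of new morphologic evidence of disease in BM". No rule is given for a rise in marrow already involved at entry.

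**PET (8.1, footnote 4-B).** These patients need a PET within 2 weeks before therapy and "should also be followed with PET scans if positive at diagnosis". Section 12.3.3.7 uses the same time point when it permits PET alongside CT for following response.

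**Spleen (12.8.4).** For PR, "Spleen must have regressed by >50% in length beyond normal". For PD with splenomegaly, "the splenic length must increase by 50% of the extent of its prior" enlargement, which is counted beyond baseline. Otherwise, "If no prior splenomegaly, must increase by at least 2 cm from baseline". Baseline is not defined for the spleen.

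**Elsewhere.** The Abstract describes the population as recurrent or refractory. The neuroblastoma marrow rules (12.5.3 and 12.6.1) refer to enrollment. Section 4.0 asks for marrow, when applicable, within 14 days before therapy.

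**The concern.** Response on a single-arm trial should be a change since treatment started. For a relapsed patient, the state at diagnosis reflects an earlier phase of disease and earlier treatment. The PR definition uses diagnosis for marrow and baseline for PET, so a reader cannot safely assume that the two words mean the same time.

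The marrow clause matters when a response is called, because note 6 to the Section 8.1 table asks for marrow when CR or PR is seen in target disease. A call made against the wrong time point could remove a real responder or admit a doubtful one, and the primary rule turns on 3 responses in 20. A spleen PD call would also be a PFS event and a ground for removal from therapy (10.1). Langerhans cell histiocytosis and non-Hodgkin lymphoma are both listed in Appendix VII as possible expansion histologies.

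**Working it through.** The plan gives no figure on this point, so the rules are applied to assumed cases. The percentages and lengths below are assumptions, not trial data.

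**1. Marrow absent at diagnosis, present at entry.** Diagnosis 0%, entry 20%, on study 10%.
- Reduction from entry: 1 − 10/20 = 50%, so the amount is met.
- Residual disease is allowed only if it was there at diagnosis. It was not, so PR is barred.
- This needs no assumption about the reference for the 50%.

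**2. Marrow rising since entry.** Diagnosis 80%, entry 20%, on study 35%.
- Reduction from diagnosis: 1 − 35/80 = 56%, which passes.
- Change from entry: 35/20 − 1 = +75%, which fails.
- The marrow PD rule in 12.8.2 covers new disease only and does not clearly catch this rise. By contrast, 12.6.1 gives neuroblastoma a rule for marrow involved at enrollment: a doubling and at least 25% tumor.

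**3. No change between diagnosis and entry.** 30%, 30%, then 15% on study: 1 − 15/30 = 50% on either reading. The wording matters only when the two times differ.

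**4. PET.** A patient PET-positive before treatment but not at diagnosis is, read literally, outside the follow-up instruction. Yet CR in 12.8.2 needs a negative PET, and PD can be called on increased uptake from baseline.

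**5. Spleen.** Assume a normal length of 9 cm and 13 cm at entry. PD needs growth of 0.5 × the prior increase.
- Baseline read as study entry, first assessment: 0.5 × (13 − 13) = 0 cm.
- Prior increase counted from normal, as in the PR row: 0.5 × (13 − 9) = 2.0 cm.
- No prior splenomegaly: 2 cm, as stated.

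On the study-entry reading, an enlarged spleen has a zero threshold while a normal one has 2 cm.

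**6. What one misclassified patient does to the primary rule (11.3.1: N = 20, at least 3 responses, 5% versus 25%).** X is binomial.

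| Case | Formula | Result |
|---|---|---|
| Rule as planned, true rate 5% | P(X ≥ 3; 20, 0.05) | 7.5% |
| One patient falsely counted as responder | P(X ≥ 2; 19, 0.05) | 24.5% |
| Rule as planned, true rate 25% | P(X ≥ 3; 20, 0.25) | 90.9% |
| One patient barred from responding | P(X ≥ 3; 19, 0.25) | 88.9% |

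The first and third rows agree with the plan's alpha of 10% (as a cap) and power of 90%.

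**The case against.** A reader might infer four stronger things.

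*Worsening marrow passes as PR.* The text does not say so. Diagnosis governs only whether residual disease is permitted; the 50% clause has no stated reference. A false PR would also need a 50% SPD fall, no new disease or PD, two determinations (12.9) and central review (11.5). Section 12.2 calls progression in any established lesion PD, and 12.8.3 does the same for clear progression of non-measured lesions. Those two rules could stop a large rise, but neither names marrow or gives a threshold. So case 2 is a gap on one reading, not a demonstrated error.

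*Marrow clear at entry and positive again on study can be PR.* It should not be. If new is judged from entry, the PD rule applies and the PR definition excludes it.

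*Trivial spleen growth is PD.* This depends on reading baseline as study entry. The row speaks of a prior increase in a patient with splenomegaly, so a pre-disease length is a plausible meaning. Only the inconsistency between the rows, and the missing definition, are shown.

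*The wording departs from the published criteria.* Section 12.8 adopts outside criteria that cannot be consulted here, so that cannot be judged.

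On PET, the footnote may loosely mean the scan that it has just required, and it does not forbid further scans. A missing follow-up PET could keep a patient from CR, but one who meets PR still counts as a responder, so no loss of ORR is shown.

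What survives is case 1, which follows from the literal text, together with the unstated marrow reference, the PET time point and the unreconciled spleen rows.

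**Conclusion.** The reference points in Section 12.8 and footnote 4-B are unsuited to a relapsed population, or undefined, and should be corrected. The firmest finding is that disease which reached the marrow only after diagnosis cannot qualify for PR, even when it is halved on treatment. The opposite error, a marrow rise accepted within PR, is possible only if the reduction is read from diagnosis and no other progression rule is applied.

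The effect is confined to lymphoma/histiocytosis patients with marrow disease, a PET status that changed since diagnosis, or an enlarged spleen. The marrow clause speaks of lymphoma cells, so it is narrower still. The documents do not give the number of such patients, and it is probably small. The shifts of 7.5% to 24.5% and 90.9% to 88.9% would follow from any single misclassified patient; they show the sensitivity of a 3-of-20 rule and are not estimates of what will happen.

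**What to change.** - In 12.8.2 (marrow PR), footnote 4-B of 8.1 and 12.3.3.7, replace the reference to diagnosis with study baseline.
- In 12.8.2, state that the 50% marrow reduction is measured from the pre-treatment study sample.
- In 12.8.4, define baseline for the spleen and reconcile the PR and PD rows. Because PD leads to removal from therapy, which threshold applies is for the study team to settle against the criteria that it adopts.

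The cost is a few words in four places. Section 4.0 already calls for the pre-treatment marrow when applicable, and footnote 4-B already calls for the PET. Marrow is required only when involvement is suspected (note 5 to the 8.1 table), so a line is needed on patients with no entry sample. The downside is a few extra follow-up PET scans in patients who were positive at entry but not at diagnosis.

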#### No Response (Stable Disease)

Neither sufficient shrinkage to qualify for PR nor sufficient increase to qualify for PD, taking as reference the smallest sum diameters while on study.

#### Progressive disease

For those with > 25% increase in SPD on CT or MRI, Deauville score 4 or 5 on FDG-PET with increase in lesional uptake from baseline, or development of new morphologic evidence of disease in BM

### 12.8.3 Evaluation of Non-measured Lesions (CT-based response, PET/CT based response not applicable)

Complete Response (CR): Absent non-measured lesions.

Partial response (PR): Absent/normal, regressed, lesions, but no increase.

Stable Disease (SD): No increase consistent with progression

Progressive Disease (PD): New or clear progression of preexisting non-measured lesions.

### 12.8.4 Evaluation of organ enlargement

Complete Response (CR): Regress to normal

Partial response (PR): Spleen must have regressed by >50% in length beyond normal

Stable Disease (SD): No increase consistent with progression

Progressive Disease (PD): In the setting of splenomegaly, the splenic length must increase by 50% of the extent of its prior

increase beyond baseline. If no prior splenomegaly, must increase by at least 2 cm from baseline.

New or recurrent splenomegaly

**12.9 Best Response**

Two objective status determinations of disease status, obtained on two consecutive determinations, separated by at least a 3 week time period, are required to determine the patient's overall best response. Two objective status determinations of CR before progression are required for best response of CR. Two determinations of PR or better before progression, but not qualifying for a CR, are required for a best response of PR. Two determinations of stable/no response or better before progression, but not qualifying as CR or PR, are required for a best response of stable/no response; if the first objective status is unknown, only one such determination is required. Patients with an objective status of progression on or before the second evaluations (the first evaluation is the first radiographic evaluation after treatment has been administered) will have a best response of progressive disease. Best response is unknown if the patient does not qualify for a best response of progressive disease and if all objective statuses after the first determination and before progression are unknown.

**12.9.1 Evaluation of Best Overall Response**

The best overall response is the best response recorded from the start of the treatment until disease progression/recurrence (taking as reference for progressive disease the smallest measurements recorded since the treatment started). The patient's best response assignment will depend on the achievement of both measurement and confirmation criteria.

Table 5. Sequences of overall response assessments with corresponding best response.

1st Assessment	2nd Assessment	Best Response
Progression		Progressive disease
Stable, PR, CR	Progression	Progressive disease
Stable	Stable	Stable
Stable	PR, CR	Stable
Stable	Not done	Not RECIST classifiable
PR	PR	PR
PR	CR	PR
PR, CR	Not done	Not RECIST classifiable
CR	CR	CR

**12.9.2 Duration of Response**

Duration of overall response: The duration of overall response is measured from the time measurement criteria are met for CR or PR (whichever is first recorded) until the first date that recurrent or progressive disease is objectively documented (taking as reference for progressive disease the smallest measurements recorded since the treatment started).

The duration of overall CR is measured from the time measurement criteria are first met for CR until the first date that progressive disease is objectively documented.

Duration of stable disease: Stable disease is measured from the start of the treatment until the criteria for progression are met, taking as reference the smallest measurements recorded since the treatment started, including the baseline measurements.

### 13.0 ADVERSE EVENT REPORTING REQUIREMENTS

Adverse event data collection and reporting which are required as part of every clinical trial, are done to ensure the safety of patients enrolled in the studies as well as those who will enroll in future studies using similar agents. Adverse events are reported in a routine manner at scheduled times during a trial. (Please follow directions for routine reporting provided in the Case Report Forms for this protocol). Additionally, certain adverse events must be reported in an expedited manner to allow for optimal monitoring of patient safety and care. The following sections provide information about expedited reporting.

Reporting requirements may include the following considerations: 1) whether the patient has received an investigational or commercial agent; 2) whether the adverse event is considered serious; 3) the grade (severity); and 4) whether or not hospitalization or prolongation of hospitalization was associated with the event.

An investigational agent is a protocol drug administered under an Investigational New Drug Application (IND). In some instances, the investigational agent may be available commercially, but is actually being tested for indications not included in the approved package label.

#### 13.1 Expedited Reporting Requirements – Serious Adverse Events (SAEs)

**Any AE that is serious qualifies for expedited reporting.** An AE is defined as any untoward medical occurrence associated with the use of a drug in humans, whether or not considered drug related. A Serious Adverse Event (SAE) is any adverse drug event (experience) occurring at any dose that results in ANY of the following outcomes:

- 1) Death.
- 2) A life-threatening adverse drug experience.
- 3) An adverse event resulting in inpatient hospitalization or prolongation of existing hospitalization (for  $\geq 24$  hours). This does not include hospitalizations that are part of routine medical practice.
- 4) A persistent or significant incapacity or substantial disruption of the ability to conduct normal life functions.
- 5) A congenital anomaly/birth defect.
- 6) Important Medical Events (IME) that may not result in death, be life threatening, or require hospitalization may be considered a serious adverse drug experience when, based upon medical judgment, they may jeopardize the patient or subject and may require medical or surgical intervention to prevent one of the outcomes

listed in this definition.

#### 13.1.1 Reporting Requirements - Investigator Responsibility

Clinical investigators in the treating institutions and ultimately the Study Chair have the primary responsibility for AE identification, documentation, grading, and assignment of attribution to the investigational agent/intervention. It is the responsibility of the treating physician to supply the medical documentation needed to support the expedited AE reports in a timely manner.

**Any medical documentation supporting an expedited report (eg, H & P, admission and/or notes, consultations, ECG results, etc.) MUST be faxed within 48-72 hours to the NCI. NOTE: English is required for supporting documentation submitted to the numbers listed below in order for the NCI to meet the regulatory reporting timelines.**

Fax supporting documentation for AEs related to investigational agents supplied under a CTEP IND to: [contact]).

Also: Fax or email supporting documentation to COG for all IND studies ([contact]; email: [[contact]](mailto:[contact]); Attention: COG AERS Coordinator).

- **ALWAYS include the ticket number on all faxed documents.**
- **Use the NCI protocol number and the protocol-specific patient ID provided during trial registration on all reports.**

#### 13.1.2 CTEP-AERS Expedited Reporting Methods

Expedited AE reporting for this study must only use CTEP-AERS (Adverse Event Expedited Reporting System), accessed via the CTEP home page <https://ctepcore.nci.nih.gov/ctepaers/pages/task>.

Send supporting documentation to the NCI by fax ([contact]) and by email to both [[contact]](mailto:[contact]) and to the APEC16-21B COG Study Assigned Research Coordinator. **ALWAYS include the ticket number on all faxed and emailed documents.**

### 13.2 **Steps to Determine If an Adverse Event Is To Be Reported In an Expedited Manner**

Step 1: Identify the type of adverse event using the current version 5.0 of the NCI CTCAE. The descriptions and grading scales found in the current version 5.0 of the CTCAE will be used for AE reporting. All appropriate treatment areas should have access to a copy of the CTCAE v5.0. A copy of the CTCAE v5.0 can be downloaded from the CTEP website (<http://ctep.cancer.gov>).

Step 2: Grade the adverse event using the NCI CTCAE v5.0.

Step 3: Review [Table A](#) in this section to determine if:

- The adverse event is considered serious;
- There are any protocol-specific requirements for expedited reporting of

specific adverse events that require special monitoring; and/or

- There are any protocol-specific exceptions to the reporting requirements.
- Any medical event equivalent to CTCAE v5.0 grade 3, 4, or 5 that precipitates hospitalization (or prolongation of existing hospitalization) must be reported regardless of attribution and designation as expected or unexpected with the exception of any events identified as protocol-specific expedited adverse event reporting exclusions.
- Any event that results in persistent or significant disabilities/incapacities, congenital anomalies, or birth defects must be reported via CTEP-AERS if the event occurs following treatment with an agent under a CTEP IND.
- Use the NCI protocol number and the protocol-specific patient ID provided during trial registration on all reports.
- As referenced in the CTEP Adverse Events Reporting Requirements, an AE that resolves and then recurs during a subsequent cycle does not require CTEP-AERS reporting unless (1) the Grade increases; or (2) hospitalization is associated with the recurring AE.
- Some adverse events require notification **within 24 hours** (refer to Table A) to NCI via the web at <http://ctep.cancer.gov> (telephone CTEP at: **[contact]** within 24 hours of becoming aware of the event if the CTEP-AERS 24-Hour Notification web-based application is unavailable). Once internet connectivity is restored, a 24-hour notification phoned in must be entered electronically into CTEP-AERS by the original submitter at the site.
- When the adverse event requires expedited reporting, submit the report **within 5 or 7 calendar days** of learning of the event (refer to Table A).

**Table A: Phase 1 and Early Phase 2 Studies: Expedited Reporting Requirements for Adverse Events that Occur on Studies under an IND/IDE within 30 Days of the Last Administration of the Investigational Agent/Intervention**

FDA REPORTING REQUIREMENTS FOR SERIOUS ADVERSE EVENTS (21 CFR Part 312)  NOTE: Investigators MUST immediately report to the sponsor ANY Serious Adverse Events, whether or not they are considered related to the investigational agent(s)/intervention (21 CFR 312.64)  An adverse event is considered serious if it results in ANY of the following outcomes:
 
 
1) Death
 
2) A life-threatening adverse event
 
3) An adverse event that results in inpatient hospitalization or prolongation of existing hospitalization for <math>\geq</math> 24 hours
 
4) A persistent or significant incapacity or substantial disruption of the ability to conduct normal life functions
 
5) A congenital anomaly/birth defect.
 
6) Important Medical Events (IME) that may not result in death, be life threatening, or require hospitalization may be considered serious when, based upon medical judgment, they may jeopardize the patient or subject and may require medical or surgical intervention to prevent one of the outcomes listed in this definition. (FDA, 21 CFR 312.32; ICH E2A and ICH E6).
 
		

ALL SERIOUS adverse events that meet the above criteria MUST be immediately reported via CTEP-AERS within the timeframes detailed in the table below.
		
Hospitalization	Grade 1 and Grade 2 Timeframes	Grade 3-5 Timeframes
Resulting in Hospitalization $\geq$ 24 hrs	7 Calendar Days	24-Hour 5 Calendar Days
Not resulting in Hospitalization $\geq$ 24 hrs	Not required	

NOTE: Protocol specific exceptions to expedited reporting of serious adverse events are found in the Specific Protocol Exceptions to Expedited Reporting (SPEER) portion of the CAEPR.  Expedited AE reporting timelines are defined as:
 
 
o "24-Hour; 5 Calendar Days" - The AE must initially be reported via CTEP-AERS within 24 hours of learning of the AE, followed by a complete expedited report within 5 calendar days of the initial 24-hour report.
 
o "7 Calendar Days" - A complete expedited report on the AE must be submitted within 7 calendar days of learning of the AE.
 
		

Serious adverse events that occur more than 30 days after the last administration of investigational agent/intervention and have an attribution of possible, probable, or definite require reporting as follows:  Expedited 24-hour notification followed by complete report within 5 calendar days for:
 
 
• All Grade 3, 4, and Grade 5 AEs
 
 
Expedited 7 calendar day reports for:
 
 
• Grade 2 AEs resulting in hospitalization or prolongation of hospitalization
 
 
 For studies using PET or SPECT IND agents, the AE reporting period is limited to 10 radioactive half-lives, rounded UP to the nearest whole day, after the agent/intervention was last administered. Footnote "1" above applies after this reporting period.
		

Effective Date: May 5, 2011
		

